Date: October 8, 2013

Principal Investigator: [name]., M.A.

Application Number: NA_00088107

Study Title:

SMART Study: Scotopic Microperimetric Assessment of Rod Function in Stargardt Disease

JHM IRB - eForm A – Protocol

- **Use the section headings to write the JHM IRB eForm A, inserting the appropriate material in each. If a section is not applicable, leave heading in and insert N/A.**
- **When submitting JHM IRB eForm A (new or revised), enter the date submitted to the field at the top of JHM IRB eForm A.**

1. Abstract

- a. Provide no more than a one-page research abstract briefly stating the problem, the research hypothesis, and the importance of the research.

Stargardt disease [1] is responsible for 7% of all retinal dystrophies and affects 1 in 10,000 people. The typical onset occurs during the first two decades of life, which makes it the most common form of juvenile macular degeneration with an estimated incidence of 10 – 12.5 per 100,000. STGD has been associated with considerable clinical and genetic heterogeneity, nearly two thirds of the cases are caused by several mutations in the ABCA4 gene [2, 3] with predominantly autosomal recessive inheritance [4]. A minor percentage have been associated with mutations in the ELOVL4 and PROM1 genes [5, 6] and was linked to autosomal dominant Stargardt-like phenotypes [7], which usually have later onset [8].

In STGD, the visual acuity impairment is accompanied by atrophic-appearing lesions in the macula and presence of yellow-white lesions at the level of the retinal pigment epithelium (RPE), also known as “fundus flecks”. Histologically, these fundus flecks are characterized by sub-retinal deposition of lipofuscin-like material mainly formed from the abnormal photoreceptors’ visual cycle [9-12]. Multiple lines of evidence indicate that the toxic effect of lipofuscin accumulation in the RPE is responsible for the RPE cells death [13-15]. Following the RPE loss, photoreceptor cells (rods and cones) degenerate rapidly [16] as their maintenance is largely dependent on RPE cells.

It was surprising that first reports of ABCA4 expression found its presence in rod but not in cone photoreceptors [17]. Such findings contradicted the STGD most common clinical manifestations, which are primarily related to cones dysfunction. Only few years later, it was shown by immunofluorescence microscopy and Western blot analysis that ABCA4 is also expressed in the fovea, and so, both cones and rods express the defective gene [18]. Studies with electroretinography (ERG) confirmed the findings of ABCA4 expression in both types of photoreceptors by showing abnormal electro-activity of cone and rods. For example, [name] and collaborators have found that L and M-cone driven ERG exhibit phase and amplitude alterations in STGD [19]. Others studies with ERG have also demonstrated ERG rod dysfunction [20], although important variability in the degree of cone and rods dysfunction are frequently seen across STGD patients. The association between clinical phenotype and ERG phenotype has been previously attempted by some investigators [20]. A study conducted by Simonelli et al has shown reasonable correlation between clinical appearance and full-field ERG findings, however, such association was not supported by a later study with a larger cohort of patients [21].

Moreover, the marked phenotype (clinical appearance) variability, variable autosomal traits and large amount of mutations involving the ABCA4 gene make the correlation between gene mutations and phenotype a challenge for retina physicians. Furthermore, the differential impairment of rods and cones activity during the natural course of STGD is yet to be fully understood. It is possible that rod photoreceptors show the earliest functional decline, show regional variability of dysfunction and different rate of progression as compared to cones dysfunction. Such aspects may play important role in possible therapeutic targeting, clinical trial planning and outcomes interpretations. Whereas ERG is capable of detecting the differential rod and cone’s electrical activities, it cannot be precisely correlated with focal anatomical changes and distinguish macular lesions.

A relatively novel technology, the automated fundus related perimetry technology (also known as microperimetry-MP), constitutes a surplus tool to assess retinal function, in this case sensitivity, with the advantage of precisely correlating the retinal sensitivity to the anatomical changes seen in scanning laser ophthalmoscope (SLO) images and autofluorescence images. In the last 5 years, many studies using MP have reported cross-sectional findings of retinal sensitivity impairment in STGD [22-25]. The majority of these findings were based on the evaluation of microperimetric mesopic response (cones and rods response combined) without any consideration to differential activity and impairment of the two types of photoreceptors during the natural course of the disease.

More recently, Crossland and colleagues followed by Birch and colleagues have described and validated protocols to measure rod sensitivity using a modified MP-1 [26, 27], which may allow, for the first time, the precise evaluation of rod function and its correlation with morphologic damage in the natural history of STGD.

Ultimately, the understanding of the differential impairment of the cone and rods photoreceptors, through microperimetry findings, may establish consistent and reliable parameters to monitor patients and investigate potential treatments for STGD, which thus far, has not been available for patients with ABCA4-related retinal disease.

2. Objectives (include all primary and secondary objectives)

Through a multicenter prospective cohort study on the natural history of STGD (the ProgStar Study), this ancillary study has the main objective of investigating the rod photoreceptors' sensitivity during the natural course of the disease.

The primary objective is:

- To assess the yearly rate of progression of STGD using macular sensitivity under scotopic testing conditions.

The secondary objectives are:

- To correlate scotopic microperimetric changes with anatomical status/progression as determined by visual acuity, ERG, optical coherence tomography (OCT) and autofluorescence images.
- To determine the variability of the test.
- To determine the earliest functional deficits in STGD
- To establish the best microperimetric parameters to monitor patients with STGD.

3. Background (briefly describe pre-clinical and clinical data, current experience with procedures, drug or device, and any other relevant information to justify the research)

Device: NIDEK MP-1S (NIDEK Technologies Srl, Italy; holding company, NIDEK Co., Ltd. Japan)

In 2002, Nishida and colleagues described for the first time an automated measuring system for fundus perimetry [28]. The MP-1 microperimeter produced by NIDEK Technologies was the first commercial microperimeter garnished with a true eye-track system, replacing the manual correction for eye movements which allowed accurate quantification of sensitivity and spatial location of the points tested [29, 30].

The device is composed of an infrared fundus camera, which acquires real-time fundus images in up to 45 deg of view (768 × 576 pixels resolution). A liquid crystal display (LCD) with set luminance of 1.27cd/m² (4abs) presents the fixation target and the stimuli, which is generated and controlled by a computer [31]. At the end of the exam, a conventional fundus camera captures a standard full color image. The built-in software superimposes the visual field map onto the retinal image, providing the spatial correlation between the anatomic landmarks and visual sensitivity maps [30, 32, 33]. The perimeter software also allows customization of the test parameters, the overlay of the fixation test results onto the fundus image, re-test of the same area scanned in a previous visit and automated comparison between exams.

The MP-1 received FDA 510(k) clearance in September 28 of 2006 (510k No. K023719) and was classified as a class II device. It has been approved for color retinography, fixation exam, fundus-related MP and visual rehabilitation.

Normative data has been published by Springer and co-authors [34] and Midena and collaborators [35] facilitating the interpretation of results obtained in diseased individuals. In addition, Chen and colleagues contributed with information regarding the test-retest variability of MP in patients with macular retinopathy as measured by the MP-1 [36]. In 2011, Crossland and colleagues validated for the first time a protocol for MP evaluation under scotopic conditions [26]. Fixation patterns have also been described in patients with various macular diseases using the MP-1 microperimeter [31, 37-40].

Physicians interested in the study of psychophysical parameters rapidly incorporated the technology employed in the MP-1, contributing vast literature over the last decade. Moreover, macular sensitivity and fixation stability have become measures to evaluate patients in clinical routine. Also, low vision rehabilitation could be enhanced with training sessions for fixation relocation [40].

MP has been shown to be a good tool to enhance the understanding of functional impairment in STGD. The information gathered from this proposed study should provide guidance and support to the identification of the most appropriate clinical outcome measures for anticipated clinical trials.

4. Study Procedures

This study will assess the scotopic macular sensitivity determined by rod cells using controlled fundus perimetry under dark-adapted conditions. This test will be performed in addition to the standard of clinical care tests required in the IRB approved prospective ProgStar-02 Study (JHU IRB NA# 00081134). Only one eye will be enrolled in the SMART study. In case both eyes are eligible and are enrolled in the ProgStar-02 study, the

principal investigator (PI) will choose one eye (study eye - SE) to participate in the SMART study. The following SE selection criteria are recommended, although the final decision will be at the PI's discretion:

→ Recommended SE selection criteria:

- a) The eye that has the smaller lesion within the range defined in the ProgStar-02 protocol
- b) The eye that has the better vision in terms of best-corrected visual acuity (BCVA)
- c) The eye that has the better fixation stability, which is defined by the smaller bivariate contour ellipse area (BCEA).

- a. Study design, including the sequence and timing of study procedures (distinguish research procedures from those that are part of routine care). Study duration and number of study visits required of research participants.

This is a prospective longitudinal observational study. The study shall utilize up to 12 clinical sites to collect prospective longitudinal observations on up to 70 participants. To qualify for this study, participants be enrolled in the IRB approved ProgStar Study. The scotopic MP will be the sole non-standard of care procedure executed at each visits.

The study will collect data every 6 months over a 24 months period. Therefore, 5 visits will take place during the study (baseline, months 6, 12, 18 and 24). If enrollment and prospective evaluation of an eligible patient in the ProgStar-02 study started significantly earlier than the start of the SMART study, then it is possible that only 18 months of follow-up will be available. The last ProgStar-02 visit should also be the last SMART study visit. Each visit, all patients will undergo microperimetric examination under scotopic condition in addition to the standard of care procedures included in the ProgStar Study protocol, which are described below:

- best-corrected visual acuity,
- complete ophthalmic exam (including dilated fundoscopy),
- autofluorescence imaging,
- MP and
- spectral-domain optical coherence tomography (SD-OCT) will be performed).

The ProgStar study results will be sent by the participating centers to the Dana Center for of Preventative Ophthalmology of the Wilmer Eye Institute, the Johns Hopkins University, Baltimore, for evaluation, with exception of the results of MP, autofluorescence and optical coherence tomography, which will be sent to a central reading center at the Doheny Eye Institute, Los Angeles, California.

This is a natural history study. There will be no treatments being investigated in this trial.

- b. Blinding, including justification for blinding or not blinding the trial, if applicable. N/A
- c. Justification of why participants will not receive routine care or will have current therapy stopped. N/A
- d. Justification for inclusion of a placebo or non-treatment group. N/A
- e. Definition of treatment failure or participant removal criteria. N/A
- f. Description of what happens to participants receiving therapy when study ends or if a participant's participation in the study ends prematurely. N/A

5. Inclusion/Exclusion Criteria

Inclusion criteria:

- A mandatory inclusion criteria for the index ancillary study is being a participant of the IRB approved ProgStar Study (JHU IRB NA# 00081134). In the ProgStar Study, the study participants are required to meet the following inclusion criteria:
 1. Provide a signed informed consent form and authorization allowing the disclosure and use of protected health information.
 2. The designated primary study eye must have at least one well-demarcated area of atrophy as imaged by fundus autofluorescence with a minimum diameter of 300 microns and all lesions together must add to less than or equal to 12 mm² (equivalent to no more than 5 disc areas in a least one eye) and a BCVA of 20 ETDRS letters (20/400 Snellen equivalent) or better.
 3. Two (2) pathogenic mutations confirmed present, in the ABCA4 gene. If only one ABCA4 allele contains a pathogenic mutation, the patient shall have a typical Stargardt phenotype, namely at least one eye must have flecks at the level of the retinal pigment epithelium typical for STGD.

4. The primary study eye must have clear ocular media and adequate pupillary dilation to permit good quality FAF and sd-OCT imaging in the opinion of the investigator.
5. Be able to cooperate in performing the examinations.
6. Be willing to undergo ocular examinations once every 6 months for up to 24 months.
7. Be at least six years old.
8. Both eyes can be included if inclusion criteria are fulfilled for both eyes.

In addition, candidates of the ProgStar study that meet any of the following exclusion criteria shall not be enrolled in any of the ProgStar study neither in the index ancillary study:

1. Ocular disease, such as choroidal neovascularization, glaucoma and diabetic retinopathy, in either eye that may confound assessment of the retina morphologically and functionally.
2. Intraocular surgery in the primary study eye within 90 days prior to baseline visit.
3. Current or previous participation in an interventional study to treat STGD such as gene therapy or stem cell therapy. Current participation in a drug trial or previous participation in a drug trial within six months before enrollment. The use of oral supplements of vitamins and minerals are permitted although the current use of Vitamin A supplementation shall be documented.
4. The site Principal Investigator may declare any patient at their site ineligible to participate in the study for a sound medical reason prior to the patient's enrollment into the study.
5. Any systemic disease with a limited survival prognosis (e.g. cancer, severe/unstable cardiovascular disease).
6. Any condition that would make adherence to the examination interfere with the patient attending their regular follow-up visits schedule of once every 6 months for up to 24 months difficult or unlikely, e.g. personality disorder, use of major tranquilizers such as Haldol or Phenthiazine, chronic alcoholism, Alzheimer's Disease or drug abuse.
7. Evidence of significant uncontrolled concomitant diseases such as cardiovascular, neurological, pulmonary, renal, hepatic, endocrine or gastro-intestinal disorders.

6. Drugs/ Substances/ Devices

- a. The rationale for choosing the drug and dose or for choosing the device to be used.

Degeneration of the photoreceptors and underlying RPE in STGD typically occurs close to and within the macula center, leading to bilateral central atrophy.

MP is a valuable tool to perform a systematic and quantitative evaluation of the macular sensitivity to different intensities of light and at the same time to correlate the functional findings to anatomical changes. The Nidek MP device has a built-in eye-tracking system and permits the precise re-test of previous scanned areas [31]. In addition, this technology can provide quantitative analysis of gaze fixation, a known parameter of visual quality, which can be affected by the growth of central atrophy in patients with STGD.

The microperimeter manufactured by Nidek (MP-1, NIDEK Technologies Srl, Italy) MP-1 has been used since 2002 in research and clinical settings [28, 29] and has normative and disease data available. The device created the standards for automated fundus related perimeter and stands as the most common microperimeter found in retina services. At this time, the Nidek MP-1 is the only microperimeter that has been adapted to scotopic MP with validated protocols [41][35].

- b. Justification and safety information if FDA approved drugs will be administered for non-FDA approved indications or if doses or routes of administration or participant populations are changed. N/A
- c. Justification and safety information if non-FDA approved drugs without an IND will be administered. N/A

Date: _ June 11, 2013

Principal Investigator: _ [name]., M.A.

Application Number: _____

7. Study Statistics

- a. Primary outcome variable.
Change in macular sensitivity measured under scotopic conditions.
- b. Secondary outcome variables. N/A
- c. Statistical plan including sample size justification and interim data analysis.

Sample Size and Power:

The ancillary study will follow the statistical standards imposed by the ProgStar Study protocol.

In the ProgStar Study, a feasibility survey was undertaken prior to establishing the study protocol. The survey consisted of a questionnaire that was sent to the participating centers to determine how many study candidates might be available at each center for this prospective study.

The primary outcome of the study is the yearly growth in the area of the atrophic lesion as measured by fundus auto-fluorescence. A recent paper by Chen et al [29] reported that in a group of 24 STGD participants with well defined atrophic lesions at baseline, the mean yearly growth of the lesion was $0.94 \text{ mm}^2 \pm 0.87$.

The reliability of measuring areas of geographic atrophy using images taken with a confocal scanning laser ophthalmoscopy has been described by Deckert et al [35]. Using 2 different readers to examine images from 34 eyes, the mean difference in area affected for the proposed quantification algorithm was 0.12 mm^2 with a 95% confidence interval (0.02, 0.22).

Using the above parameters as a reference, we calculated the power to detect yearly progression for sample sizes between 120 and 240 participants, with standard deviations between 0.9 and 1.1, and expected progression rates of 0.40 and 0.50 mm^2 per year (Figure 5). A clinically meaningful progression rate should be greater than the variability of the measurement. The power calculations were set to test for progression rates above 0.2 mm^2 which is the estimate of the upper bound of the difference that could be attributable solely to measurement error.

Figure 5: Power calculations for expected progressions rates of 0.40 and 0.50 mm^2 per year

A sample size of 170 achieves 80% power to detect a difference of 0.2 between the null hypothesis mean of 0.2 mm^2 (measurement error) and the alternative hypothesis mean progression of the lesion of 0.4 mm^2 with an estimated standard deviation of 0.9 and a significance level $\alpha = 0.05$ using a two-sided Wilcoxon test (Figure 5 (a)). Similarly, if the expected standard deviation increases to 1.0 we need 200 participants to achieve the same level of power. When the expected progression rate is $\geq 0.50 \text{ mm}^2$, a sample size of 120 participants achieves more than 80% to detect differences beyond the expected measurement error, for standard deviations ≤ 1.1 (Figure 5 (b)).

Statistical Analyses

Estimating the yearly growth in the area of the atrophic lesion as measured by fundus auto-fluorescence:

First exploratory analysis looking at the baseline, six, and twelve months overall distribution of the outcome will be performed, outliers and inconsistent measures will be identified and reviewed. Let Y_{iv} represent the area (or a transformation to achieve normality; e.g. square root) of the i th individual at visit v for $v=0, 1, 2, 3, 4$ for the baseline, 6 months, 12 months, 18 months and 24 months visits, respectively. In order to determine the average rate of progression in the population, an appropriate approach will be to allow for each individual to have his/her own intercept and slope and to average them to achieve the overall rate of decline. This is accomplished with a random coefficients regression model of the form:

$$Y_{iv} = (\mu + a_i) + (\Delta + b_i)v + \gamma Z_{iv} + e_{iv}; \text{ where } a_i \sim N(0, \sigma_1^2), b_i \sim N(0, \sigma_2^2), \text{ cov}(a_i, b_i) = \sigma_{12} \text{ and } e_{iv} \sim N(0, \sigma^2).$$

The a_i and b_i are the random departures of the line for the i th individual from the population line with intercept μ and slope Δ . The e_{iv} are the within individual departures from the line of the repeated measurements taken on the i th individual at times 0, 6, 12, 18 and 24 months. Z_{iv} represents a vector of factors that could be related to progression such as age and use of vitamin A supplementation.

The estimate of Δ and its standard error will provide the six-month progression of the lesions. In addition, to explore whether progression may be different for different initial levels, we will carry out the analysis in strata of baseline severity.

A similar approach to will be used to examine progression overtime for the secondary outcomes: retinal thinning, loss of photoreceptors, loss of retinal sensitivity, and changes of BCVA.

Scatterplots with lowess smooth average curves will be used to explore the relationship between variables. A linear mixed model will be then used to analyze and quantify the association between the different variables.

Baseline demographic characteristics are: date of birth, age, sex, and race. Randomization is not applicable.

Data Set Descriptions

Study Population: patients with STGD enrolled into the study shall have had previous genetic testing and a finding of at least 2 pathogenic mutations in the ABCA4 gene. If only one ABCA4 allele containing a pathogenic mutation is detected, a patient may be enrolled if they have a typical Stargardt phenotype, i.e. at least one eye must have flecks at the level of the retinal pigment epithelium typical of STGD.

Data Sets for Endpoint Analyses: the final data set will include all participant visits. Most of the participants will complete 5 visits. Participants lost to follow-up after the six month visit shall be included but will only partially contribute to the estimation of the progression rates.

Handling of Missing Data: the random effects methods described in section 7.2 do not require all individuals to have all the five visits. Individuals who are lost to follow up will partially contribute to the analysis and will be appropriately weighted by the maximum likelihood approach. To rule out informative censoring (i.e., fast progressors having less visits with available data) we will perform sensitivity analysis restricting to those with complete data. Were it to be necessary, we will explore multiple imputation methods to complete the trajectories shorter than two years.

Interim Analysis: an interim analysis of the study data is planned after all participants have completed their 12-month visit.

d. Early stopping rules.

This is an observational study of the natural course of STGD. All devices included in the study are used in standard of clinical care for patients affected by STGD. Therefore, no study-specific safety events are anticipated.

8. Risks

a. Medical risks, listing all procedures, their major and minor risks and expected frequency.

This study is an observational study of the natural course of STGD that will include data from the results of both psychophysical examinations (visual acuity testing and microperimetry) and retinal imaging examinations (optical coherence tomography and fundus autofluorescence), which are an integral part of current standard of clinical Care that is routine in patients with STGD. The risk to participants will not exceed the risks associated with the current standard of clinical care examinations. The protocol for scotopic microperimetry does not use any range of the light spectrum that could cause known harm to patients with STGD or would put the patients above minimal risks.

b. Steps taken to minimize the risks. N/A

c. Plan for reporting unanticipated problems or study deviations.

Protocol Deviations:

This study shall be conducted according to this written protocol except in the case of an emergency where immediate intervention based on the judgment of the investigator (or a responsible, appropriately trained professional designated by the investigator) is essential for the protection, safety, and well-being of the participant. In the event of a significant deviation from the protocol as a result of an emergency, accident, or mistake, the investigator or designee must contact the Study Director, as soon as possible, by telephone. A joint decision will then be made regarding the participant's continuation in the study and

the decision documented by the investigator and the Study Director and reviewed by the monitor. In addition, the investigator must notify the IRB to the extent necessary under GCP and local requirements. The sponsor, the Foundation Fighting Blindness Clinical Research Institute shall be notified of any protocol deviations and shall forward a detailed report any serious deviations to HRPO immediately. Any non-serious deviations shall be reported to HRPO as part of the annual study progress report.

All unanticipated problems involving risk to participants or others related to participation in the study should be promptly reported to the Principal Investigator's office by [contact]).

- d. Legal risks such as the risks that would be associated with breach of confidentiality.

Although microperimetry under scotopic condition is not a standard MP protocol used in regular clinic visits of patients with ABCA4 related retinopathies, microperimetry exam is considered a standard of care procedure. The risks that would be associated with breach of confidentiality in scotopic microperimetry would not be higher than any other standard of care procedures.

If the results of the each individual's procedures conducted during the time period of patients' participation in this study, including any clinically significant abnormal findings, if requested, will be shared with that study participants or their his/her primary care provider at any time during throughout the study since study participation is part of standard clinical care and authorized by the patient.

- e. Financial risks to the participants.

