3.6.2 Study Data

Table 3.6.2 Study Data					
ASSESSMENT/ PROCEDURE DATA COLLECTION POINTS	BASELINE Visit 1 DAY 0	VISIT 2 MONTH 6	VISIT 3 MONTH 12	VISIT 4 MONTH 18	VISIT 5 MONTH 24
Informed consent, medical history, genotype information, demographics	X				
Inclusion/Exclusion criteria assessed	X				
ETDRS BCVA Data	X	X	X	X	X
Ophthalmic fundus exam ¹ Data	X	X	X	X	X
Autofluorescence imaging Data	X	X	X	X	X
Microperimetry ² Data	X	X	X	X	X
sd-OCT Data	X	X	X	X	X
Changes in medical and ophthalmic history Data	X	X	X	X	X
Vitamin A supplementation Data	X	X	X	X	X
Full-field electroretinogram ³ Data	X				
Exit from study ⁴					X

¹: Ophthalmic examination includes slit lamp examination, cataract grading, and dilated fundus examination

²: In selected centers

³: Only if a full-field ERG was not performed within the past 5 years.

⁴: If qualified, patients may exit the study before Visit 5 to participate in an investigational treatment study for STGD

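### SMART cannot identify the earliest functional deficit in Stargardt disease, because every study eye already has atrophy; at most it can describe loss at points not yet atrophic

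*Protocol*

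**What the plan says.** The objective stands without qualification in section 2 of the SMART eForm A: "To determine the earliest functional deficits in STGD". Neither what counts as earliest nor what counts as a deficit is defined. The abstract supplies the motive: rods may decline before cones, with differences by region and in rate.

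Eligibility is in section 5: "A mandatory inclusion criteria for the index ancillary study is being a participant of the IRB approved ProgStar Study". ProgStar inclusion criterion 2, reproduced there, reads: "The designated primary study eye must have at least one well-demarcated area of atrophy as imaged by fundus autofluorescence". The same criterion sets the smallest admissible lesion at 300 microns across and caps total lesion area at 12 mm². Criterion 8 adds: "Both eyes can be included if inclusion criteria are fulfilled for both eyes". Section 4 says: "Only one eye will be enrolled in the SMART study". If both eyes are eligible, it recommends the eye with the smaller lesion, still inside the ProgStar-02 range.

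Section 7b gives no secondary outcome variables (N/A). The SAP lists SMART as PROGSTAR-02a, but the only microperimetry outcome it names is mean sensitivity. It mentions no scotopic, point-level or scotopic-versus-mesopic analysis. In the PROGSTAR-02 protocol, Table 3.6.2 footnotes microperimetry with "In selected centers".

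**The concern.** Determining which function fails first requires eyes observed before the event that defines entry, or at least a reference against which an early deficit can be recognised. SMART admits only eyes that have passed that point. A deficit already present at baseline has no onset date, so a low scotopic value beside a better mesopic value would not show that rod loss came first.

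Section 3 of the eForm says the results should guide the choice of outcome measures for future trials, and the abstract ties the rod-versus-cone question to therapeutic targeting and trial planning. A statement that rod loss, or cone loss, is the earliest deficit in the disease could be carried into early-stage trials without support from this cohort.

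**Working it through.** The plan gives no figure for this objective. The power calculation in section 7c of the eForm concerns lesion area on autofluorescence and has no bearing on it. The check is mainly a reading of the passages side by side, with some arithmetic on lesion size.

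**1. Can any SMART eye be seen before atrophy?**
- SMART participant implies ProgStar participant (eForm, sections 4 and 5).
- The ProgStar primary study eye has at least one well-demarcated lesion of 300 microns or more (criterion 2).
- A second eye enters only if it meets the same criteria (criterion 8), so it has atrophy too.
- SMART takes one eye. The investigator's discretion applies between two eyes that are both eligible and enrolled.
- Result: 0 of up to 70 study eyes are observed before atrophy. Entry acuity may be as low as 20 letters, so substantial loss can already be present.

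**2. Is there a source of pre-atrophic or reference data elsewhere?**
- Concurrent controls: none are planned.
- PROGSTAR-01 (Figure 6) allows earlier visits without a lesion, but that study is retrospective and describes no scotopic test.
- Published MP-1 norms are cited in eForm section 3, but the text does not say that they are scotopic.
- Full-field ERG gives separate rod and cone responses. It is scheduled at baseline only, a result up to five years old is accepted, and the SMART abstract itself says ERG cannot be matched precisely to focal anatomical change.

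**3. How much non-atrophic retina do eligible eyes contain?**
- Smallest lesion: π × (0.15 mm)² = 0.071 mm².
- Share of the ceiling: 0.071 / 12 = 0.6%. One disc area is 12 / 5 = 2.4 mm², so the smallest lesion is 0.071 / 2.4 = 0.03 disc areas.
- The test grid is not given. Assume a circular field of 12 to 20 degrees at 0.29 mm per degree. The area is then π × (3.48/2)² = 9.5 mm² to π × (5.80/2)² = 26.4 mm².
- Atrophic share at the smallest lesion: 0.071 / 26.4 = 0.3% to 0.071 / 9.5 = 0.7%. At 12 mm², if all of it lies in the field: 12 / 26.4 = 45% up to 100%.

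**4. Can points be seen before they become atrophic?**
- The eForm says microperimetry locates sensitivity on the fundus image and that the software can return to an area tested before.
- Section 7c cites mean growth of 0.94 mm² per year and uses 0.40 to 0.50 for power. Over 24 months that is 2 × 0.40 = 0.80 mm² to 2 × 0.94 = 1.88 mm² per eye.
- Retina that turns atrophic in that time, if it lies under test points, is observed beforehand at point level.

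**5. Does point-level follow-up recover the order of onset?** Not as planned. A point outside atrophy at baseline may already be impaired on one or both tests. Dating the first loss requires points normal on both tests at entry, hence a scotopic reference range and a threshold, and neither is specified. The SMART abstract also describes the mesopic response as that of rods and cones together, so scotopic against mesopic is not a clean rod-against-cone contrast.

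**The case against.** The strongest reply is that the instrument measures points, not eyes. Steps 3 and 4 show that many eligible eyes have ample retina outside atrophy that can be followed for up to 24 months, and the recommended choice of the smaller lesion and better acuity favours earlier-stage retina. The abstract speaks of regional differences and relative rates, so the earliest loss in retina not yet atrophic is a fair reading of an undefined word. The objective is also only one of several secondary ones, with no hypothesis test attached.

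Much of this stands. A reader might infer that the objective cannot be pursued in any form, or that no participant contributes any pre-atrophic observation. The documents do not support that: the count of 0 holds for eyes, not for points. A reader might also infer that no usable scotopic norm exists, but the cited sources cannot be checked here, so that remains open.

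The reply does not rescue the objective as worded. Loss in spared retina of an eye with atrophy answers a different question from what fails first in the disease, and the plan defines no outcome, reference range or analysis for the narrower question either.

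**Conclusion.** The concern holds in a limited form. As designed, SMART cannot identify the earliest functional deficit in the course of Stargardt disease: all of its up to 70 study eyes enter with atrophy of at least 300 microns, and the scotopic test is given to no pre-atrophic eye and no concurrent control. It can at most describe loss at points not yet atrophic in eyes that already have atrophy.

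This conclusion rests on the eligibility text alone. The field-size shares in step 3 depend on an assumed grid and conversion, and serve only to show that the narrower question is feasible in many eyes. The primary objective is not affected.

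**What to change.** Replace the objective in section 2 of the eForm with: *To describe, in eyes with atrophy and at test points outside FAF-defined atrophy at baseline, the yearly change in scotopic and in mesopic sensitivity.*

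Add to the SAP:
- Mixed models with points clustered within eyes, restricted to eyes that have both tests. Table 3.6.2 limits ProgStar microperimetry to some centers, whereas section 4a of the eForm lists it at each visit for all patients.
- Each slope in its own dB scale per year, with a confidence interval.
- Slope divided by within-eye residual SD only as a separate index of how readily each test detects change. It must not be read as showing which function declines faster: with equal true loss, the noisier test would appear to decline more slowly.
- A statement that the mesopic response combines rods and cones, that order of onset cannot be inferred, and that results do not extend to pre-atrophic disease.

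No extra visits or participants are needed, but the change has costs. The objective becomes narrower and test points must be registered to FAF. The documents give no test grid and do not say that scotopic and mesopic points coincide, so both need to be settled first. Keeping the objective as now worded would instead require a pre-atrophic ABCA4 group and controls on the same scotopic test, which is a larger study.
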